Predictability and Aversive Expectancies in Anxiety and Depressive Disorders
03-M-0093 October 4, 2021

Identifying Words: Anxiety disorders, generalized anxiety disorder, panic disorder, agoraphobia, fear conditioning, context conditioning, startle, psychophysiology

[name], Ph.D.: Section on the Neurobiology of Fear and Anxiety
National Institute of Mental Health
[name]
[name]
[name]
[contact]
E-mail: [contact]

Total requested accrual: 1271

Healthy volunteers:	663
Patients	608
Sub-study 1: 110 patients	44 healthy volunteers
Sub-study 2: 115 patients	86 healthy volunteers
Sub-study 3: 38 patients	38 healthy volunteers
Sub-study 4: 30 patients	30 healthy volunteers
Sub-study 5: 30 patients	30 healthy volunteers
Sub-study 6: 30 patients	
Sub-study 7: 40 patients	40 healthy volunteers

Project uses ionizing radiation: no

IND/IDE: no

Durable power of attorney: no

Multi-institutional project: no

Data and Safety Monitoring Board: no

Technology Transfer Agreement: no

Samples are being stored: yes

Flesch Kincaid reading level of consents

Control: 7.3
Cognition: 8.4

PRECIS

High-generalized anxiety is a concomitant of many anxiety disorders and is often regarded as a vulnerability marker for these disorders (Barlow, 1988). One characteristic of patients with anxiety disorders and high trait-anxious individuals is inappropriate expectancies of aversive events. The overall aim of the present protocol is to investigate mechanisms that may promote the development of these aversive expectancies using expectancy-based, associative-learning models.

During aversive conditioning in which a phasic explicit-cue (e.g., a light) is repeatedly associated with an aversive unconditioned-stimulus (e.g., a shock), the organism develops fear to the explicit cue as well as to the environmental context in which the experiment took place. We have obtained preliminary evidence suggesting that contextual fear represents aspects of aversive states that are central to anxiety disorders (Grillon, Ameli, Goddard, Woods, & Davis, 1994; Grillon & Morgan, 1999; Grillon, Morgan, Davis, & Southwick, 1998). In this protocol, we seek further evidence for the relevance of contextual fear to mood and anxiety disorders.

1. INTRODUCTION

Fear and anxiety are normal adaptive responses to threat. Anxiety is considered pathological when it is either excessive or inappropriate to the context. Thus, pathological anxiety could result from overactive structures involved in responses to threat, abnormal relational learning (conditioning), or from inefficient affective information processing that prevents an organism from effectively implementing goal-directed behaviors. The present protocol builds on our past results to study the impact of induced anxiety (e.g., during anticipation of shock) on physiological and subjective measures on fear and anxiety and on task performance in patients with mood and anxiety disorders.

1- Past studies

One past objective was to better understand aversive conditioning processes in anxiety disorders. We have reported 1) increased stimulus generalization in panic disorder (Lissek, et al., 2010), 2) relational learning deficits in panic disorder (Grillon, Lissek, [name], McDowell, & Levenson, 2007), and 3) heightened conditioning with socially relevant stimuli in social anxiety disorder (Lissek, et al., 2008).

Another objective was to study the processes that separate fear and anxiety. While fear is a phasic response associated with an identifiable source that is thought to predict occurrence of an aversive stimulus, anxiety is a more persistent feeling of apprehensive anticipation of future danger (Barlow, 1988). We have demonstrated that the characteristics of these two forms of aversive responses – cued fear and generalized anxiety - could be modeled by administering predictable and unpredictable aversive events (shocks), respectively (Grillon, 2002; Grillon & Davis, 1997). Fear is operationally defined as an increase in startle amplitude during a threat cue that predicts an aversive event (fear-potentiated startle). Anxiety is operationally defined as an increased in startle amplitude during long periods of unpredictable aversive events (anxiety-potentiated startle). One of the past objectives of this protocol was to examine far-potentiated startle and anxiety-potentiated startle in anxiety disorders. We have found that patients with panic disorder and PTSD, but not generalized anxiety disorder (GAD), showed elevated anxiety-potentiated startle (Grillon, et al., 2008; Grillon, et al., 2009). Given that the underlying neural mediators of fear and anxiety are partially distinct (amygdala versus bed nucleus of the stria terminalis) (Davis, Walker, Miles, & Grillon, 2010), these results provide clues to potential pathophysiological mechanisms and targets for treatment.

2- Current studies

We are currently pursuing this line of research to address new questions. As indicated above we found increased anxiety-potentiated startle in PTSD and panic disorder but not GAD. Failure to obtain increased anxiety-potentiated startle in GAD may have been due to the use of mildly aversive stimuli (e.g., airblasts). We are currently examining whether more potent aversive stimuli such as shocks will lead to elevated anxiety-potentiated startle in GAD. We are also examining the specificity of the heightened anxiety-potentiated startle in patients with various types of anxiety disorders (e.g., social anxiety disorder). We are also testing patients with major depression (MDD) and bipolar disorder (BP) of contradictory finding regarding fear-potentiated startle and more generally emotional responses to

aversive stimuli in MDD. While MDD has been associated with a blunting of emotional responses not only to positive stimuli but also to negative stimuli, and reduced fear-potentiated startle in studies that use mildly evocative emotional stimuli (McTeague, et al., 2009) we have reported that depressive mood increased anxiety-potentiated startle (Robinson, Overstreet, Letkiewicz, & Grillon in press) during shock threat. This protocol will clarify whether MDD is associated with emotional blunting or with increased fear and/or anxiety.

Anxiety and Cognition

Our past research has mainly focused on response expression. Our new objective is to examine the interaction between induced anxiety, goal-directed behaviors, and emotional pathology. Anxiety can be adaptive, but it can be debilitating when it interferes with our daily life and our goals. High levels of anxiety have been associated with poor performance and processing inefficiencies on cognitive tasks (Eysenck & Calvo, 1992) suggesting that cognitive changes may be a key component of clinical anxiety. Yerkes and Dodson proposed that the detriment in performance due to high emotional arousal (e.g., anxiety) can be described by a U-shaped function, where performance increases as arousal increases to an optimal level and then as arousal levels continue to increase, performance begins to decrease (Yerkes & Dodson, 1908). In support of this proposal, high trait anxious individuals (i.e., those with an above-optimal level of emotional arousal) have been shown to experience disruption in executive processes (Eysenck & Calvo, 1992) and in the ability to perform at work, which can lead to career dissatisfaction and job loss. However, the mechanisms by which performance is affected (e.g., attentional narrowing, executive processing deficiencies, perceptual focus), and the degree to which performance is reliably hindered or facilitated by anxiety is not clear. The current study will allow us to address this gap in our knowledge. Inarguably, understanding the link between emotion and cognition in patient groups with emotional pathology is of particular importance to the development of successful therapeutic interventions.

We will focus on the interaction between anxiety and working memory (WM). WM is the ability to maintain relevant information in mind and to keep irrelevant information out of mind. As such, WM will enable us to examine two of the main symptoms of anxiety, inability to focus and increased distractibility. Anxiety may be especially detrimental to WM by decreasing one's ability to keep irrelevant anxious thoughts out of mind, hence compromising efficient information processing. It has been suggested that high-load cognitive tasks may be more susceptible to anxiety-related disruption (Eysenck, Derakshan, Santos, & Calvo, 2007). This proposal, known as the processing efficiency theory (Eysenck & Calvo, 1992), is based on the claim that the deleterious effects of anxiety on cognition are greatest when task demands are high because the executive processing resources that subserve working memory are also engaged by worrisome thoughts. In contrast to Eysenck et al., (2007)'s cognitive theory, Bishop has argued that anxiety has a greater impact on perceptual tasks that place a lower demand on processing resources, while tasks that place a higher demand on resources reduce the deleterious impact of anxiety (Bishop, 2008). In order to lend clarity to these competing views, we will investigate the extent to which induced-anxiety interferes with WM as memory load increases (using n-back and digit span tasks described below). Further, we will investigate the impact of anxiety on spatial versus verbal WM, using a verbal and spatial n-back task and the Corsi test (another visuospatial test of WM). Previous research suggests that spatial WM tasks may be more susceptible to anxiety-related disruption when anxiety is

induced in healthy subjects (Shackman et al. 2006; Vytal et al., 2013). However, it is unclear whether or not pathological anxiety results in a similar pattern of disruption. By addressing this question, we will be better informed about the nature of anxiety-related disruption and be closer to delineating the mechanisms of such disruption.

While the detrimental effect of anxiety on cognition is well-known, less is known about how task performance affects anxiety. However, it is clear that being engaged in a WM task is an effective way of reducing anxiety. One of the aims of this protocol will be to examine whether patients with mood and anxiety disorders can similarly use WM engagement to reduce anxiety.

In contrast to WM where anxiety appears to be only detrimental, there is evidence to suggest that the anxiety can both impair and facilitate performance on sustained attention tasks (e.g., Go-NoGo task). It is unknown whether anxiety acts a distractor, impairing response inhibition to infrequent “NoGo” trials (resulting in commission errors), or whether anxiety improves the ability to withhold these prepotent responses. Some research suggests that commission errors are the result of “mind wandering” ([Smallwood et al., 2004](#)), which may be increased when subjects are anxious. Other research suggests that anxiety can increase inhibition of motor responses (prepulse inhibition; [Grillon and Davis, 2007](#)), which would lead to better performance when subjects are anxious. Here we hope to clarify whether or not pathological anxiety impairs or facilitates performance on non-emotional sustained attention tasks.

2. STUDY OBJECTIVES

- a. Objective 1: To examine fear-potentiated startle and anxiety-potentiated startle in mood and anxiety disorders. To what extent does heightened anxiety-potentiated startle cut across distinct anxiety disorders? Are fear-potentiated startle and anxiety-potentiated startle also elevated in mood disorders?
- b. Objective 2: To examine the interaction between induced-anxiety and WM as cognitive load increases. Does anxiety affect WM performance and is this effect dependent on cognitive load? Can patients with mood or anxiety disorder reduce their anxiety by being engaged in a WM task?

3. SUBJECTS

a. Description of Study Populations

- Participants will be 18 to 50 years old and will be diagnosed with one of the following: generalized anxiety disorder, panic disorder, SAD, specific phobias, major depression, and bipolar depression according to DSM-IV. Patients on scheduled/regular psychotropic medications, other than lithium or Depakote, will stay on their medication. Although patients will not be taken off medications for the purposes of this study, included patients will not be currently taking psychiatric medications or any other medications that may interfere with study results (see exclusion criteria for other characteristics of patient sample). The only

exception is that bipolar depressed patients may be taking mood stabilizers, either lithium carbonate or Depakote. Subjects taking PRN medication that is allowed according to the medication table below, must be both willing and safely able to hold the medication for 5 half-lives. Additionally, healthy controls who are age and sex matched to patients will be studied.

- The accrual ceiling is 608 patients with mood or anxiety disorders and 663 healthy volunteers. This accrual ceiling includes a drop out/withdrawal/non-analyzable data rate of 15% for sub-studies 1 (11 patients, 44 controls) and 2 (115 patients, 86 controls) and 25% for sub-study 3 (38 patients, 38 controls).
- NIH, but not NIMH, employees may participate. NIH employee participation is guided by intramural institute policy.

b. Inclusion criteria for both patients and healthy controls

- All subjects must be able to give written informed consent prior to participation in this study.
- PATIENTS ONLY: May have DSM-IV-TR diagnoses of an anxiety disorder (GAD; SAD; Panic disorder; specific phobia) or mood disorder (MDD; BP).
- PATIENTS ONLY: May be taking the mood stabilizers, Depakote or Lithium Carbonate.
- Speaks English fluently
-

c. Exclusion criteria for healthy subjects

- Female subjects who are currently pregnant
- Subjects who meet DSM-IV criteria for current alcohol or substance abuse
- Subjects with a history of alcohol or substance dependence within 6 months prior to screening
- Current Axis I psychiatric disorders as identified with the Structured Clinical Interview for DSM-IV-TR axis disorders, non-patient edition (SCID-np). Past history of any psychotic disorder or bipolar disorder.
- IQ < 80
- Medical illnesses (such as diabetes or hypertension) or neurological illnesses (such as carpal tunnel syndrome for shocks to be delivered on affected arm; organic brain impairment; seizure disorder) likely to interfere with the study.
- Subjects who are on a medication that may interfere with the study (see Table below).
- Employee of NIMH or an immediate family member who is a NIMH employee.

d. Exclusion criteria for patients

- Patients who would be unable to comply with study procedures or assessments;
- Female patients who are currently pregnant;
- Patients who meet DSM-IV criteria for current alcohol or substance abuse

- Subjects with a history of alcohol or substance dependence within 6 months prior to screening;
- Patients who are on a medication (other than mood stabilizers lithium carbonate or Depakote) that may interfere with the study (see Table below).
- Medical illnesses (such as diabetes or hypertension) or neurological illnesses (such as carpal tunnel syndrome; organic brain impairment; seizure disorder) likely to interfere with the study.
- Patients will be excluded if they have a current or past history of, delirium, dementia, amnestic disorder, any of the pervasive developmental disorders; or cognitive impairment.
- Current Axis I psychiatric disorders as identified with the Structured Clinical Interview for DSM-IV-TR axis disorders, non-patient edition (SCID) with the exception of the mood and anxiety disorders. Past history of any psychotic disorder or bipolar disorder.
- IQ < 80
- Employee of NIMH or an immediate family member who is a NIMH employee.

e. Additional exclusion criteria for the active avoidance task

- Color blindness

Table of drug exclusions for both healthy volunteers and patient volunteers (Y=acceptable; N=exclusion). Excluded medications are those that are known to cross the blood brain barrier and/or affect physiological responses (ex: beta blockers like Inderal, antihistamines like Benadryl or systemic corticosteroids like cortisone).

Drug Class	Episodic Use (p.r.n.)	Chronic Use	Restrictions
Analgesics	Y	N	Non-narcotic analgesics only Ex. Advil (Ibuprofen), Tylenol (Acetaminophen)
Antacids	Y	Y	e.g., Zantac (Ranitidine) except episodic (p.r.n.) use, is acceptable if subject has not taken medication for 5 half-lives prior to study
Antiangular Agents	N	N	
Antiarrhythmics	N	N	
Antiasthma Agents	Y	Y	Systemic corticosteroids are not allowed e.g., Cortisone
Antibiotics	Y	N	
Anticonvulsants	N	Y	For bipolar subjects – only Depakote or lithium permitted
Systemic Antifungal Agents	N	N	Acceptable for episodic (p.r.n.) use if subject has not taken the medication for 5 half-lives prior to study visit
Antihypertensive	N	Y	Except for Beta-Blockers, e.g., Inderall (Propranolol) or Lopressor/Toprol (metoprolol)

Antihistamines -Sedating	Y	N	Sedating: e.g., Benadryl (Diphenhydramine), Sudafed PE (diphenhydramine), Alka-Setzer and Aller-Chor (chlorpheniramine) as long as the subject has not taken in the last 5 half-lives prior to the study visit
Antihyperlipidemics	N	Y	e.g., Zocor (simvastatin,)
Anti-inflammatory Drugs	Y	Y	Systematic corticosteroids are NOT allowed, e.g., Cortisone
Antivirals	N	N	Except for treatment of HSV with agents without CNS activity e.g., Zovirax (acyclovir), Cytovene(ganciclovir), Famvir (famciclovir), Valtrex (valacyclovir)
Cough/Cold Preparations	Y	N	Non-sedating antihistamines are allowed (e.g.Zyrtec-D (cetirizine), Claritin-D or Alavert-D (loratadine) and Allegra (fexofenadine) Dextromethorphan preps N/N Guanfacine Y/Y Pseudoephedrine N/N e.g., Nyquil, Dayquil or Mucinex preparations, that include sedating antihistamines, are acceptable if subject has not taken the medication for 5 half-lives prior to study visit
Hormones	N	Y	Only thyroid hormone replacement, oral contraceptives, and estrogen replacement therapy are allowed.
Muscle Relaxants Psychotropic Medication	N Y	N N	e.g., Flexeril (Cyclobenzaprine) Acceptable for episodic (p.r.n.) use if subject has not taken the medication for 5 half-lives prior to study visit.

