f. Experimental Procedures. A series of procedures designed to minimize risk will be applied to participants in this protocol. Both patients and healthy controls will undergo a sample shock procedure before any experiments involving electric shock are run to assess each individual’s reaction to the shock, to adjust the shock to a level that is well tolerated, and to give the participant a chance to withdraw from the study if they so wish. An additional procedure is the observation of participants by way of a non-recording video camera and two-way audio telecom throughout testing. Participants are instructed to signal the experimenter through the video camera or by calling the experimenter’s name at any point during the experiment if they wish to end the experiment or if they wish to speak with the experimenter for any reason. Upon completion of testing procedures for a given visit, patients with a psychiatric disorder are evaluated by [name] to assess for any adverse reactions to experimental procedures. Hence, any problems that stem from these procedures will also be detected and treated in a timely manner.

g. Delayed Treatment. Although anxiety and mood patients will not be taken off any medication for the purposes of this study, we will only include those patients who are not

currently taking psychotropic medications. The only exception to this is the bipolar depressed patients. These individuals, because of the risks associated with mood destabilization, will be permitted to continue taking either Depakote or lithium carbonate as mood stabilizers. Nonetheless, patients included in this study may be at risk of symptom worsening because of the absence of other psychopharmacologic treatment. If patients choose to enroll in the study despite this risk, their symptoms will be monitored by medical staff. If symptoms worsen and are deemed by our medical staff to be a threat to the patient's welfare, the patient will be discontinued from the study and receive brief treatment by our medical staff while referral efforts to community care are underway.

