[name]'s role will include serving as the intervening psychiatrist in the event of adverse reactions or symptom worsening as well as delivering short-term treatment (1-2 months, not to exceed 3 months) to anxiety patients upon their completion of the protocol. Additionally, [name] will complete the initial psychiatric evaluation (described below) and will be on call for subjects along with other psychiatrists on the child anxiety on-call schedule to allow 24-7 on call coverage for patients in this protocol. In the event that participating patients experience symptom worsening while off-campus, they will call the child anxiety on-call schedule. When [name] is the on call-physician, he will provide the psychiatric treatment for this patient. Otherwise, the on-call physician at the time the patient calls will intervene and provide the necessary care. [name] and his associates in his program will serve as the primary treating psychiatrists for depressed patients in this protocol. [name] or a clinician in his group will be the primary treating physicians. They will intervene in the event of adverse reactions or symptom worsening and will as deliver appropriate treatment.

- **Healthy Controls:** Throughout experimental procedures, psychiatrically healthy subjects will be monitored by both a non-recording video camera and by a two-way audio telecom. Procedures will be stopped for any subject who asks to stop any procedure at any point. Subjects will be asked if they wish to continue with other phases of the study. Procedures will also be stopped for any subject who exhibits signs of distress during any phase of the study. At this point, subjects will be interviewed to confirm that they are in fact in distress and psychiatric intervention will follow when necessary. Subjects will be asked if they wish to continue with other phases of the study.
- **Psychiatric Patients:** Mood patients accepted into this protocol will have been thoroughly screened and assessed for inclusion/exclusion criteria by clinicians of the Experimental Therapeutics & Pathophysiology Branch of NIMH. For English speaking bipolar depressed patients, [name] and his team will be responsible for screening evaluations, the experiments and clinical assessments during each visit.

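### The patient exclusion list, read as written, shuts out the bipolar patients whom the rest of the protocol makes eligible and analyses as a group

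*Combined protocol and SAP*

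**What the plan says.** The patient exclusions in Section 3.d contain one bullet made of two sentences. The first excludes current Axis I disorders other than mood and anxiety disorders. The second excludes on history and has no exception: "with the exception of the mood and anxiety disorders. Past history of any psychotic disorder or bipolar disorder". Section 3.c, for healthy volunteers, ends its corresponding bullet the same way: "non-patient edition (SCID-np). Past history of any psychotic disorder or bipolar disorder".

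Elsewhere the protocol plans for bipolar patients:

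- Section 3.a lists bipolar depression among the qualifying diagnoses and makes a medication allowance for it: "exception is that bipolar depressed patients may be taking mood stabilizers".
- Section 3.b, inclusion: "May have DSM-IV-TR diagnoses of an anxiety disorder (GAD; SAD; Panic disorder; specific phobia) or mood disorder (MDD; BP".
- The drug table in Section 3 has an entry for bipolar subjects in the anticonvulsants row: "only Depakote or lithium permitted".
- Section 7.g says of bipolar depressed patients that they "will be permitted to continue taking either Depakote or lithium carbonate as mood stabilizers".
- Section 8 assigns responsibility for their screening and assessment: "For English speaking bipolar depressed patients".
- Section 10 names bipolar disorder, with MDD and controls, as a level of the Group factor in the mood-disorder ANOVAs of Sub-studies 1 and 2.

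**The concern.** The exemption for mood disorders belongs to the sentence on current disorders. Nothing carries it into the sentence on history. A patient with an established bipolar diagnosis ordinarily has a history of bipolar disorder, so a screener who applies 3.d as written would exclude the patient whom 3.b admits, or would enrol the patient and create an eligibility deviation.

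If the rule were applied literally, the mood-disorder ANOVA in each of Sub-studies 1 and 2 would shrink to MDD against control. The mood-disorder part of Objectives 1 and 2 would then rest on MDD alone in those sub-studies. The separate anxiety-disorder ANOVAs would not be touched.

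The sentence looks carried over from the healthy-volunteer list. The patient bullet also names the non-patient edition of the SCID, although Section 4.c reserves that edition for non-patients.

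**Working it through.** **Does the sample size count a bipolar group?** The inputs are from Section 10. Sub-study 1 needs 18 evaluable per group, allows 15% unusable data, recruits 22 per group, and totals 110 patients and 44 controls. Sub-study 2 needs 20 evaluable per group, allows 15%, recruits 23 per group, and totals 115 patients and 46 controls (before the 40 pilot controls). The diagnostic groups are GAD, SAD and panic disorder in one analysis, and MDD and bipolar in the other: five in all, with controls in each analysis.

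Reproducing the plan's figures:

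- Sub-study 1: 18 / (1 − 0.15) = 21.2, rounded up to 22. Patients 5 x 22 = 110; controls 2 x 22 = 44. Both match.
- Sub-study 2: 20 x 1.15 = 23. Patients 5 x 23 = 115; controls 2 x 23 = 46. Both match. (Dividing by 0.85, as fits Sub-study 1, would give 24; this does not bear on the present point.)

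Without a bipolar group the totals would be 4 x 22 = 88 and 4 x 23 = 92, which are not the stated totals. So the plan counts bipolar patients as one of five groups.

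**Size of the loss on the literal reading:**

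| | Sub-study 1 | Sub-study 2 |
|---|---|---|
| Bipolar places lost | 22 | 23 |
| Share of all patients | 22/110 = 20% | 23/115 = 20% |
| Share of mood-disorder patients | 22/44 = 50% | 23/46 = 50% |
| Evaluable in mood ANOVA, as planned | 3 x 18 = 54 | 3 x 20 = 60 |
| Evaluable in mood ANOVA, no bipolar group | 2 x 18 = 36 | 2 x 20 = 40 |

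Together, 22 + 23 = 45 of 110 + 115 = 225 patient places (20%), or 45/608 = 7.4% of the protocol's patient ceiling. These are places, not persons, because Section 10 lets a participant join more than one sub-study.

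Section 10 plans between-group contrasts in Sub-study 1. Three mood groups give three pairs. Without the bipolar group one pair remains (MDD against control), and the two involving bipolar patients cannot be made. Section 10 sets out no pairwise contrasts for Sub-study 2; there the Group factor falls from three levels to two.

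**Loss on the alternative reading.** If current bipolar disorder is exempt as a mood disorder and only a past, non-current history excludes, the loss is zero and 110 and 115 stand.

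**The case against.** The best defence is that the bullet contrasts current with past. Current bipolar depression is a mood disorder and is exempt; the second sentence then reaches only people whose bipolar disorder is not current. The preceding bullet in 3.d gives this some support, since it writes "current or past history of, delirium, dementia" when both are meant. The medication bullet of 3.d also excepts lithium and Depakote, an allowance that 3.a ties to bipolar depressed patients, so the same list contemplates them. Mood-disorder patients are referred by a specialist group already charged with screening bipolar patients (Sections 4.b and 8), and that group is unlikely to turn all of them away. The documents report no such exclusion or deviation.

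Much of this stands. The intent to enrol is plain, and the full loss of 45 places is not the expected outcome. Objectives 1 and 2 speak of mood disorders without naming bipolar disorder, so losing the group would narrow them and not leave them unanswered. The 22 and 23 bipolar places are inferred from the per-group numbers; no separate bipolar quota is stated.

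What does not stand is that the text already says this. The current-versus-past reading has to be inferred, and it sits poorly with Section 7.g, where bipolar patients continue a mood stabilizer and so would normally have a bipolar history. The list is also applied to mood patients by clinicians of another branch, and Section 16 provides for audits at least once every three years. Both are reasons for the written criterion to be unambiguous.

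**Conclusion.** The concern holds: as written, 3.d conflicts with the eligible population in 3.a and 3.b and with the bipolar group in the Sub-study 1 and 2 analyses. Read literally, it removes 22 of 110 and 23 of 115 patient places, and leaves the mood-disorder ANOVAs with 36 of 54 and 40 of 60 evaluable participants. That assumes equal groups at the stated per-group numbers. On the alternative reading the loss is zero. The likelier practical harm lies between these: bipolar patients screened differently by different staff, and enrolments recorded as deviations. It should be corrected, but it is not evidence that the bipolar group was dropped or that any patient was turned away.

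**What to change.** Amend the second sentence of the 3.d bullet so that the bipolar-history exclusion does not apply to patients whose qualifying diagnosis is bipolar disorder, in any sub-study open to mood-disorder patients. If only a past, non-current bipolar history was meant to exclude, say that explicitly. Check the result against 3.a, 3.b, the drug table, 7.g, the Psychiatric Patients paragraph of Section 8 and the Group factors in Section 10, so that eligibility text, analysis groups and patient totals agree. Leave 3.c as it is.

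The cost is a one-sentence protocol amendment. No patients, procedures or analyses are added, and the totals of 110 and 115 do not change.
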